"Physiological" insulin scheme vs "Traditional" scheme for glycemic control in non-critical hospitalized patients with Type 2 Diabetes Mellitus: Controlled Clinical Trial

Registration number: NCT03350984

Date: 02/08/2019

MATERIAL AND METHOD

TYPE OF STUDY:

- Clinical controlled trial, randomized, not blinded, comparative between 2 groups.

WORKING UNIVERSE

- Patients with diabetes mellitus type 2.

SAMPLING FRAME

- Hospitalized patients in the medical and surgical services of the hospital: internal medicine, traumatology and orthopedics and general surgery of the General Hospital of León not critical with diabetes mellitus type 2.

SAMPLE SIZE

- It was determined a minimal sample size of 33 patients per group plus 7 extra patients in each group to compensate possible losses, which gave a total of 40 per group. The sample size was determined by the formula: $n=(Z\alpha/2+Z\beta)^2 * (p_1(1-p_1)+p_2(1-p_2)) / (p_1-p_2)^2 \cdot (36)$ It was considered the probability of making a mistake type 1 (α) of 0.05, a statistical potential ($1-\beta$) of 0.80 and a difference of 25% in the rate of hypoglycemia in reference with the one reported in the meta-analysis of Christensen MB et al(27), for both treatments in a bicaudal way in the distribution curve.

SAMPLING TYPE

- Randomized systematic sampling. The assignment to the treatment schemes was made using a randomized numbered table generated by a computer. If more of one patient arrived to the hospital at the same time, they were randomized in order of the service they arrived: Internal medicine (IM): 1st, Traumatology and orthopedics (TyO): 2nd and General surgery(GS): 3rd, and in base of the number of bed from lower to higher.

INCLUSION CRITERIA

- Patients older than 18 years old, with diagnosis of diabetes type 2 with central fasting glucose before randomization between 140mg/dl and 400mg/dl.
- Patients that were diagnosed at admission with DM2 with HBA1>6.5% and fasting glucose >126mg/dl (isolated hyperglycemia >200mg/dl was not considered as a diagnostic parameter because of the stress conditions, metabolic response to the base pathology or steroid exposition that can alter the glycemia values in hospitalized patients).
- Patients in not critical state.
- Patients with a diet for diabetic patient per oral administration at least 3 times

daily.

EXCLUSION CRITERIA

- Parenteral nutrition and continuous enteral nutrition by nasogastric tube.
- Chronic kidney disease with a glomerular filtration rate <15mg/dl or in renal replacement therapy.
- Hyperosmolar state or diabetic ketoacidosis.
- Diabetes mellitus type 1
- Hyperglycemia due to stress (negative history of DM2, hyperglycemia and HbA1C<6.4)
- - Parenteral nutrition and continuous enteral nutrition by nasogastric tube.
- - Chronic kidney disease with a glomerular filtration rate <15mg / dl or in renal replacement therapy.
- - Hyperosmolar state or diabetic ketoacidosis.
- - Diabetes mellitus type 1.
- - Hyperglycemia due to stress (negative history of DM2, hyperglycemia and HbA1 <6.4)
- - Treatment with any steroid equivalent to more than 10mg of prednisone.
- - Pregnancy.
- - CHILD PUGH C hepatic failure
- - Acute pancreatitis.
- - Sepsis, septic shock or multiple organ failure.

ELIMINATION CRITERIA

- Patient who is discharged by voluntary discharge.
- Patient who, due to their clinical condition that causes aggression (frontal syndrome, psychotic state, alcohol withdrawal syndrome, etc.), prevents the application of their treatment.

PROCEDURE

- Patient selection:

Once the protocol was approved by the HGL committee, the selection of patients was initiated; those who met the inclusion and exclusion criteria were invited to participate in the study with prior informed consent (Annex 2). Upon entry to the floor of internal medicine, general surgery and trauma, a record sheet was filled out with the data, which included weight, height, central glucose levels and glycosylated hemoglobin. Patients that were not diagnosed but with HbA1> 6.5 were also included in the study.

- Assignment of the groups:

Patients with diabetes or with HbA1> 6.5% were assigned to the insulin scheme

according to a systematic randomization which was done by means of a table of random numbers generated by a computer, as they were entering the different floors of internal medicine, general surgery or traumatology. The assigned scheme was placed in the internal part of the folders of indications and vital signs of each patient. The emblem of "Patient in protocol" highlighted with a striking color was the identifier of patients in protocol.

-Patient monitorization

At least one sample of central glucose and one HbA1c determination were taken at the time of admission to the protocol. A fasting blood glucose was taken every day, 2 hours after breakfast, before lunch, before dinner and 2 hours after dinner, as well as capillary blood glucose at midnight at 3 am. The data obtained were recorded on the nursing working sheet.

- About the control of diet and calories for patients

Upon entering the protocol, a standardized diet for patient with diabetes was assigned to each patient with a caloric intake of 1600 to 2000 kcal depending on the requirements for body weight, calculated by the nutrition staff. The distribution was 50% of carbohydrates, 30% of lipids and 20% of proteins. In those patients who continued with hyperglycemia and didn't have control with a standardized diabetic diet, an individualized diet was performed, for which an energy requirement calculation was made 25-30 kcal/kg and in patients with obesity 20 kcal/kg. The distribution of carbohydrates 45-55% and lipids 25-35%, proteins 15-25%.

A food ration was provided at breakfast between 8 - 9hr, another at 14 - 15hr and another at approximately 20-21hr.

For patients who showed a tendency to hypoglycemia, in addition to the insulin adjustment, snack foods were indicated by the nutrition service. The assistance of family members and nurses was requested to ensure that the ration of their food was finished. In those patients who presented episodes of hypoglycemia associated with not finishing their food, designated insulin scheme was suspended.

-Protocol of insulin treatment and management of hypoglycemia:

1. Schematic "Physiological"

A. Patients previously treated with insulin or patients who were not treated on an outpatient basis with insulin (oral diet or hypoglycemic agents) or first diagnosis of DM2: Suspend the dose of insulin applied and stop the oral antidiabetic drugs on admission and replace them with insulin, Initiating the total daily dose: When the basal glucose is between 140 and 200 mg / dl: 0.4 IU/kg/day and between 201 and

400 mg/dl: 0.5 IU/kg/day. When the patient is susceptible to hypoglycemia events (localized infection, glomerular filtration rate of 16-30 ml/min/m², age greater than 70 years), the dose of 0.35 IU/kg/day may be initiated at the endocrinologist's consideration.

- 50% of the total insulin dose with Glargine and the other 50% with Lispro insulin fractionated according to the number of foods.
- Glargine is administered once a day, at 8 pm.
- Lispro is administered in three divided doses proportionally immediately before each meal.
- To prevent hypoglycemia, if a subject cannot eat, skip the Lispro insulin dose of that food.

B. Insulin adjustment:

- If fasting capillary glucose is <140 mg/dl in the absence of hypoglycemia: no change.
- If fasting capillary glucose is between 140 and 180 mg/dl: the total insulin dose increases by 10%.
- If fasting capillary glucose is >180 mg/dl: increase the total insulin dose by 20%.
- If fasting capillary glucose is <70 mg/dl, decrease the daily dose of total insulin by 20%.

C. Supplemental Insulin: Administer insulin Lispro according to the protocol "Complementary scheme". The scheduled insulin dose during the meal hour was supplemented with insulin lispro if basal glucose was higher than 180 mg/dl by the "complementary scheme" protocol (Annex 1). If fasting or postprandial capillary glucose persists >180 mg/day despite the previously assigned scheme:

- If a patient can eat all or most of their meals, administer supplemental insulin Lispro following the "usual" column.
- If a patient cannot eat, has a soft tissue infection, is >70 years old or has a glomerular filtration rate of 15-30 ml/min, administer supplemental insulin Lispro following the "insulin-sensitive" column.
- If the capillary glucose is persistently >180 mg/dl in the absence of hypoglycemia, increase the insulin scale from the "sensitive" to "usual" column or from the "usual" column to the "resistant" column.

2. Traditional Scheme:

A. Patients previously treated with insulin or patients who were not treated on an outpatient basis with insulin (oral diet or hypoglycemic agents) or first diagnosis of DM2: Suspend the insulin dose applied and stop the oral antidiabetic drugs on admission and replace them with insulin, initiating Total daily dose: If basal glucose

is between 140 and 200 mg/dl: 0.4 IU/kg/day. If basal glucose is between 201 and 400 mg/dl: 0.5 IU/kg/day. When the patient is susceptible to hypoglycemia (localized infection, glomerular filtration rate of 16-30 ml/min/m², age greater than 70 years), the dose of 0.35 IU/kg/day may be initiated at the endocrinologist's discretion.

- 2/3 parts of the calculated dose with NPH Insulin at 8 a.m. and 1/3 part of the dose at 8 p.m., is always administered at the same time.

- In order to prevent hypoglycemia, if a subject cannot eat, suspend the dose of NPH insulin.

B. Insulin adjustment:

- If fasting capillary glucose is <140 mg/dl in the absence of hypoglycemia: no change.

- If fasting capillary glucose is between 140 and 180 mg/dl: the total insulin dose increases by 10%.

- If fasting capillary glucose is >180 mg/dl: increase the total insulin dose by 20%.

- If fasting capillary glucose is <70mg/dl, decrease the daily dose of total insulin by 20%.

C. Supplemental Insulin: Administer supplemental insulin lispro in addition to NPH insulin programmed for baseline glucose greater than 180 mg/dL using a supplemental insulin protocol (Annex 1). If fasting or postprandial capillary glucose persists >180mg/day despite the previously assigned scheme:

- If a patient can eat all or most of their meals, administer supplemental insulin Lispro following the "usual" column.

- If a patient cannot eat, is >70 years old, soft tissue infection or has a glomerular filtration rate of 16-30ml/min, administer supplemental insulin Lispro following the "insulin-sensitive" column.

- If the capillary glucose is persistently >180 mg/dl in the absence of hypoglycemia, increase the insulin scale from the "sensitive" to "usual" column or from the "usual" column to the "resistant" column.

3. Management of Hypoglycemia

If a capillary glucose measurement of the patient has <70mg/dl, either by hourly capillary glucose or by the presence of clinical symptoms (sweating, chills, dizziness, nausea, hunger, blurred vision, numbness, paresthesia of the lips or tongue) and is alert, provide oral feeding equivalent to 15 grams of carbohydrates (1 serving of food or 1-2 tablespoons of sugar) or 30ml of 50% glucose solution.

If the patient presents altered state of consciousness (drowsiness, confusion, or stupor) or does not tolerate the oral route, apply 30ml of 50% glucose solution (15 grams of carbohydrates) and 15 minutes later take a new capillary blood glucose measurement. If glucose levels continue <70mg / dl, a new dose of 15g of

carbohydrate is applied every 15 minutes until glucose >70mg/dl is reached.

If during the study patients present more than 1 event of hypoglycemia after adjustment with a 20% decrease in insulin dose after a first event, in the absence of fasting, suspend the insulin regimen. Only restart insulin scheme in the case of disappearance of the hypoglycemia risk factor.

STATISTICAL ANALYSIS

The descriptive statistical analysis was carried out in the following way: for the qualitative variables proportions and percentage rates (%) were reported; for the quantitative variables, mean and standard deviation or median and interquartile range (Q1 to Q3) were reported according to the distribution of the data. The normality of the distribution was determined by the Kolmogorov-Smirnov test.

The univariate inferential analysis was performed using the chi-square test or Fisher's exact test for the qualitative variables, according to the distribution of the expected values in the contingency table. For the numerical variables, the t test was used for two independent samples or its non-parametric version, according to the nature of the distribution of the numerical data. A p value <0.05 was considered significant.

For the analysis of the treatment, the risk analysis model will be used with the calculation of the RR, RAR, RRR, its 95% Confidence Interval (95% CI) and the NNT was determined for the traditional scheme, once the data were concluded. The analysis was considered by protocol and by intention to treat.

RESULTS

PATIENTS OF THE STUDY

A total of 111 hospitalized DM2 patients not critical to the study were evaluated. Of these, 35 did not meet the inclusion criteria and the 76 included participants were randomized into two groups. The recruitment of patients began on November 15, 2017 and ended on June 1, 2018. The "physiological" insulin group with 37 participants and the traditional group with 39 participants. Within the "physiological" group, 1 patient was eliminated before initiating the insulin regimen, presenting acute abdomen and requiring intensive therapy. Therefore, 36 patients in the "physiological" group and 39 patients in the traditional group began treatment, who entered the analysis for intention to treat. From the physiological group 6 patients did not conclude the treatment by discharge before the control and 2 patients due to poor adherence to the treatment. In the traditional group, 5 patients withdrew before the control, 1 patient due to poor adherence to treatment, 1 patient died before the control, and 1 patient was suspended due to critical condition. At the end of the study, 28 patients in the "physiological" group and 31 patients in the traditional group were completed in the analysis per protocol. In 20 (71.4%) patients in the first group and in 30 (96.8%) patients in the second group, treatment was completed until discharge.

POPULATION CHARACTERISTICS

Of the total patients analyzed for intention to treat, 34 (45.3%) patients were men and 41 (54.7%) women. According to the place of hospitalization, 18 (24%) were in the internal medicine service, 29 (38.7%) in traumatology and orthopedics and 28 (37.3%) in general surgery. The mean age of the patients was 57.83 ± 13 years. The average body mass index was 26 ± 5.1 kg / m². The mean random glucose at admission was 230.5 ± 70.2 mg / dL, the glycosylated hemoglobin level was $8.3 \pm 2.3\%$, and the serum creatinine was 1 ± 0.5 mg / dL. The treatment before admission was with oral hypoglycemic agents in 25 (33.3%) patients, with insulin in 25 (33.3%) patients, the combination of oral hypoglycemic agents and insulin in 12 (16%) patients and 13 (17.3%) patients. they received treatment or were diagnosed at the time of admission. The average dose of insulin administered was 29.6 ± 11.6 IU and the number of days of hospital stay was 9.3 ± 5 days. The reasons for admission to the hospital were: abscesses and soft tissue infection, hip fracture, diabetic foot, other fractures, cancer, heart disease, gastrointestinal bleeding, acute cholecystitis, stage IV chronic kidney disease, pneumonia, gonarthrosis, pathway infection urinary tract, intoxications, meningitis, alveolar obesity-hypoventilation syndrome, peripheral thrombosis and obstructive uropathy.

EFFECTIVENESS RESULTS

When evaluating efficacy, by protocol, the following was observed: The fasting glucose average in the "physiological" group was 130.3 ± 20.9 mg / dl, while in the traditional group it was 126 ± 22 mg / dl ($p = 0.114$); the average postprandial glucose in the physiological group was 150.8 ± 22.8 mg / dl and in the traditional group it was 149.4 ± 28.1 mg / dl ($p = 0.833$). The average morning glucose in the first group was 130.9 ± 18.3 mg / dl and 125.9 ± 26.7 mg / dl in the second group ($p = 0.081$).

In the analysis by intent to treat in the same way control was achieved in goals in both groups. The average fasting glucose in the "physiological" group was 135 ± 22.6 mg / dl, while in the traditional group it was 129.6 ± 23.6 mg / dl ($p = 0.114$); the average postprandial glucose in the physiological group was 156.2 ± 27.2 mg / dl and in the traditional group it was 155.4 ± 29 mg / dl ($p = 0.902$). The average morning glucose in the first group was 136.2 ± 21.2 mg / dl and 127.4 ± 26.6 mg / dl in the second group ($p = 0.081$).

The number of days to reach control during the hospital stay statistically were not different between groups (by protocol 4.9 ± 2.2 days vs 4.7 ± 2.4 days, $p = 0.553$, by intention to treat 4.9 ± 2.1 days vs 4.7 ± 2.3 days, $p = 0.445$).

SAFETY RESULTS

Safety was evaluated with episodes of hypoglycemia and complications associated with diabetes. In the "physiological" group it was observed that 15 (41.6%) patients had at least one event of hypoglycemia during their entire stay; On the other hand, in the traditional group 15 (38.4%) presented at least one event of hypoglycemia (per protocol, RR: 1.11, 95% CI: 0.62 to 1.97, $p = 0.729$; intention to treat, RR = 1.08, 95% CI: 0.62 to 1.89, $p = 0.777$). The presence of more than 2 hypoglycemic events during their hospitalization was observed in 8 (22.2%) patients of the "physiological" group and in 2 (5.1%) patients of the traditional group (per protocol, RR = 7.75, 95% CI: 1.02 a 59.13, $p = 0.021$; by intention to treat, RR: 4.33, 95% CI: 0.98 to 19.07, $p = 0.041$).

In the analysis by protocol, the rate of the number of total events / patients with hypoglycemia in the "physiological" group was 2.4 ± 1.3 events / patient, while in the traditional group it was 1.6 ± 0.7 events / patient ($p = 0.129$) ; in the intention-to-treat analysis in the "physiological" group it was 2.5 ± 1.6 events / patient, whereas in the traditional group it was 1.7 ± 0.9 events / patient ($p = 0.182$).

Thirty-eight hypoglycemic events were found in the "physiological" group and 26 hypoglycemic events in the traditional group; of which, 36 were mild hypoglycemia in the "physiological" group and 24 events in the traditional group (RR per protocol: 1.02, 95% CI: 0.91 to 1.19, $p = 1.0$; RR by intention to treat: 1.03, 95% CI: 0.90 to 1.17, $p = 1.0$).

Regarding the complications associated with diabetes, soft tissue infection was the most frequent, one patient had pneumonia, one acute renal failure, one acute

respiratory failure, and no patient presented bacteremia, diabetic ketoacidosis or hyperosmolar state. Two of the patients included in the study died from complications not associated with hypoglycemia, one in the physiological group secondary to progression of the infectious process, sepsis and septic shock, and one in the group Traditionally associated with acute respiratory failure.

SECONDARY RESULTS

There was a significant difference in the sustained control of blood glucose that was reported in 20 (55.6%) of the cases in the physiological group compared to 30 (76.9%) of the traditional group (per protocol, RR: 0.74, 95% CI: 0.58 to 0.94, $p = 0.009$; by intention to treat, RR: 0.72, 95% CI: 0.51 to 1.01, $p = 0.049$).

The causes of failure of the sustained control were discharge before control in goals, progress to critical state, death before glycemic control, poor adherence to the protocol and suspension for sustained hypoglycemia. With the "physiological" scheme it was necessary to suspend or change by another scheme in 8 (22.2%) patients, in comparison with the traditional scheme where only the scheme was suspended or changed in 1 (2.6%) patient (by intention to treat, RR: 8.67, 95% CI: 1.14 to 65.92, $p = 0.011$). There were no adverse effects to the use of insulin in both groups.

OTHER RESULTS

If the suspension of the scheme is considered for sustained hypoglycemia of 8 patients in the physiological group vs 1 patient in the control group, a risk ratio of 8.67 (95% CI: 1.14 to 65.9) and a number necessary to harm of 5.09 was calculated (95% CI: 2.93 to 19.23) patients with the physiological scheme to produce 1 event of hypoglycemia.

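### In both arms the insulin adjustment rule raises the dose on fasting glucose alone, and no stated rule settles the dose after a non-fasting hypoglycaemic event

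*Combined protocol and SAP*

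**What the plan says.** The adjustment rule is part B of the physiological scheme and is repeated, in effect unchanged, as part B of the traditional scheme. It has four steps, all keyed to fasting capillary glucose:

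- Step one, which holds the dose: "If fasting capillary glucose is <140 mg/dl in the absence of hypoglycemia: no change"
- Step two, the smaller of the two upward steps: "If fasting capillary glucose is between 140 and 180 mg/dl: the total insulin dose increases by 10" (per cent)
- Step three, the larger upward step: "If fasting capillary glucose is >180 mg/dl: increase the total insulin dose by 20" (per cent)
- Step four, the sole downward step: "If fasting capillary glucose is <70 mg/dl, decrease the daily dose of total insulin by 20" (per cent)

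Only the no-change step mentions hypoglycaemia. Part C of each scheme, on supplemental lispro, does make escalation conditional: "If the capillary glucose is persistently >180 mg/dl in the absence of hypoglycemia, increase the insulin scale".

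Section 3, Management of Hypoglycemia, is wider in scope. It opens with "If a capillary glucose measurement of the patient has <70mg/dl, either by hourly capillary glucose or by the presence of clinical symptoms", and so is not confined to fasting readings. It sets out carbohydrate treatment and re-measurement, then suspends the regimen if there is "more than 1 event of hypoglycemia after adjustment with a 20% decrease in insulin dose after a first event, in the absence of fasting".

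The section on diet and calories adds a third provision: the assigned scheme is suspended when hypoglycaemia is linked to unfinished food. No sentence says which of these provisions prevails.

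**The concern.** Patients have one fasting reading a day, together with readings after breakfast, before lunch, before dinner, after dinner and overnight. A value below 70 mg/dl at one of those other times, with a fasting value of 140 mg/dl or more, is therefore a situation that the monitoring can detect. Part B followed as written raises the dose in that patient. Section 3 can be read as taking for granted that the dose was cut.

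Hypoglycaemia is the outcome on which the sample size was based. The suspension rule also sits behind a reported result: suspension or change of scheme in 8 versus 1 patients, which the Other Results section attributes to sustained hypoglycaemia and turns into a risk ratio of 8.67 and a number needed to harm of 5.09. If staff could apply the dose and suspension provisions in more than one way, a reader needs to know which way they were applied before interpreting that contrast. The trial was not blinded, so identical wording in the two arms does not by itself guarantee identical application.

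**Working it through.** The document states no figure for this divergence, so the check sets the provisions side by side and applies the stated percentages.

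**Inputs.** Part B, both arms: +10% for fasting 140–180 mg/dl, +20% above 180 mg/dl, −20% below 70 mg/dl, and no change below 140 mg/dl if there is no hypoglycaemia. Section 3: a 20% decrease, named as a precondition of suspension.

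**Two readings of section 3.** Under reading A, the 20% decrease applies to a first event whether fasting or not. Under reading B, those words refer back to the part B step for a fasting value below 70 mg/dl.

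**Patient with a non-fasting value below 70 mg/dl** (multiplier of total dose):

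| Fasting value (mg/dl) | Part B, literal | Reading A | Reading B |
|---|---|---|---|
| <70 | 0.80 | 0.80 | 0.80 |
| 70–139 | no step | 0.80 | no dose rule |
| 140–180 | 1.10 | 0.80 | 1.10, nothing opposes it |
| >180 | 1.20 | 0.80 | 1.20, nothing opposes it |

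The 70–139 row takes hypoglycaemia in the sense of section 3, so the condition on the no-change step fails and no other step applies.

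**Size of the divergence under reading A.**

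- Fasting 140–180: 1.10 / 0.80 = 1.375, a gap of 30 percentage points of the prior dose.
- Fasting >180: 1.20 / 0.80 = 1.50, a gap of 40 points.
- Illustration at the reported mean dose of 29.6 IU, assumed to be a daily total: 29.6 × 1.10 = 32.56 IU or 29.6 × 1.20 = 35.52 IU, against 29.6 × 0.80 = 23.68 IU. This shows the spread only, not which value is right.

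**How many patients it could touch.** Patients with at least one event: 15 + 15 = 30 of 36 + 39 = 75. Events: 38 + 26 = 64. These include fasting events and events at any fasting value, so they are ceilings. The affected subset is not reported.

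**The reported result that depends on suspension.** 8/36 = 22.2% and 1/39 = 2.6%. The risk ratio is (8/36) / (1/39) = 8.67. The risk difference is 0.2222 − 0.0256 = 0.1966, so the number needed to harm is 1 / 0.1966 = 5.09. Both agree with the document. It does not say whether each suspension followed from section 3 or from the unfinished-food provision.

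**The case against.** The strongest reply is that there is no second dose order. Section 3 orders carbohydrate, re-measurement and suspension; the 20% decrease appears only in a clause describing what has already happened. The sole instruction to cut the dose is the part B step for fasting values below 70 mg/dl, and the clause may simply point back to it. The diet section also speaks of adjusting insulin in patients prone to hypoglycaemia without limiting this to fasting values, which suggests that section 3 was meant to supplement part B. This stands in part: the text does not prove that two instructions contradict each other. But the harmonising reading leaves a gap in place of the conflict, because the increase steps remain unconditional and nothing in the dose rules responds to the event.

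A reader might infer several stronger claims that the documents do not support:

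- **That section 3 calls for a decrease after every first event.** The clause carries a qualifier about the absence of fasting. It may mean events not explained by missed food, or events at non-fasting times.
- **That part B escalates the dose every day.** Measurement is daily; part B gives no adjustment frequency.
- **That staff following part B could never begin counting towards suspension.** This could hold only for patients whose events were all non-fasting and whose staff read part B literally. Suspensions for sustained hypoglycaemia did occur, and their triggers are not recorded.
- **That the ambiguity biases the comparison because mealtime lispro produces more mealtime events.** Event timing by arm is not reported, and the wording is the same in both arms.

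It is also true that recruitment ended in June 2018, so rewording cannot alter conduct in this trial.

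**Conclusion.** The point holds as a defect in a stated safety rule, in both arms. Part B read literally increases insulin after a non-fasting hypoglycaemic event whenever fasting glucose is 140 mg/dl or more. Depending on how section 3 is read, this either runs opposite to a presupposed 20% decrease, with resulting doses differing by a factor of 1.375 or 1.50, or stands with no dose rule answering the event. For fasting values of 70–139 mg/dl, part B supplies no step. The guard on the supplemental scale shows that the authors could state such a condition, so its absence from the two increase steps is more than a matter of style.

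The factors rest on the stated percentages and on reading A. The finding that the increase is unguarded needs neither reading. The number of patients affected is unknown, with 30 patients and 64 events as ceilings. Nothing here shows that patients were in fact given the higher dose, or that the 8 versus 1 result is biased. It shows that the document does not give enough to tell.

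**What to change.** Reconcile the unfinished-food provision in the diet section, part B of both schemes and section 3. One stated rule should govern the dose after any hypoglycaemic event, fasting or not, and the text should say which section takes precedence and what the qualifier about the absence of fasting means. The choice of rule belongs to the sponsor's clinicians; none is proposed here. This is a change of wording and serves any reuse of the scheme.

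For this trial, tabulate by arm from the nursing sheets and dosing records:

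1. how many of the 38 and 26 events were non-fasting;
2. the fasting value and the dose change that followed each one;
3. which provision triggered each of the 8 and 1 suspensions or changes of scheme.

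Report this beside the risk ratio of 8.67. The cost is one pass through existing records for at most 64 events and 9 suspensions or changes of scheme, with no new data collection.

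### The glucose comparisons ignore admission glucose and HbA1c, which are recorded at entry: no bias, but some lost precision, and borderline results whose baseline balance cannot be checked

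*Combined protocol and SAP*

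**What the plan says.** All references are to the combined protocol and SAP.

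- **Tests (STATISTICAL ANALYSIS).** For categorical outcomes, "The univariate inferential analysis was performed using the chi-square test or Fisher's exact test for the qualitative variables". For numerical outcomes, "For the numerical variables, the t test was used for two independent samples or its non-parametric version", the choice depending on the distribution. The threshold is "A p value <0.05 was considered significant". Treatment effects are crude relative and absolute risk measures and a number needed to treat. No covariate, regression or stratified analysis is named.
- **Entry data (PROCEDURE, patient monitoring).** "At least one sample of central glucose and one HbA1c determination were taken at the time of admission to the protocol". The record sheet described under patient selection also lists both variables.
- **Allocation (SAMPLING TYPE; PROCEDURE, assignment of the groups).** A computer-generated random number table, with no stratification described.
- **Baseline (POPULATION CHARACTERISTICS).** Summaries are pooled over arms, for example "The mean random glucose at admission was 230.5 ± 70.2 mg / dL". HbA1c, age, creatinine and prior treatment are pooled in the same way.

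**The concern.** Admission glucose and HbA1c are natural candidates to predict glucose in hospital, and they cost nothing more to collect. Leaving a prognostic covariate out of a small trial has two effects. The interval for the treatment difference is wider than it need be. The particular estimate obtained also carries whatever imbalance the allocation happened to produce. The first matters because no glucose outcome separates the arms and the results give p values without a mean difference or interval. The second matters most where a conclusion rests on a p value next to 0.05, because the text gives no baseline table by arm from which to judge whether the arms started alike.

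**Working it through.** **Inputs.** Intention-to-treat numbers 36 and 39 (PATIENTS OF THE STUDY). Fasting glucose 135 ± 22.6 and 129.6 ± 23.6 mg/dl (EFFECTIVENESS RESULTS). Pooled admission glucose SD 70.2 mg/dl and HbA1c SD 2.3 points (POPULATION CHARACTERISTICS). Sustained control 20/36 and 30/39 (SECONDARY RESULTS). The correlation r between the baseline covariates and the outcome is not in the documents; I assume 0.1 to 0.5.

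**1. Reported figures.**
- Fasting: pooled SD = √[(35×22.6² + 38×23.6²)/73] = 23.1. SE = 23.1 × √(1/36 + 1/39) = 23.1 × 0.231 = 5.34. Difference 5.4, 95% CI 5.4 ± 1.993 × 5.34 = 5.4 ± 10.7, or −5.3 to 16.1. The t test gives p = 0.32; the document prints 0.114. A rank test could explain the gap, but 0.114 is also printed for the per-protocol set, where the t test gives 0.45. This needs a separate check.
- Sustained control: difference 55.6% − 76.9% = −21.4 points. Pooled SE = √(0.667 × 0.333) × 0.231 = 10.9 points, z = 1.96, chi-square p = 0.050 (printed 0.049), Fisher p = 0.085. The printed risk-ratio interval, 0.51 to 1.01, reproduces.

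**2. Size of chance imbalance (1 SD).** Admission glucose: 70.2 × 0.231 = 16.2 mg/dl. HbA1c: 2.3 × 0.231 = 0.53 points.

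**3. Precision for fasting glucose.** Adjusted half-width = 10.65 × √(1 − r²). Equivalent extra patients = 1/(1 − r²) − 1. Shift from a 1-SD imbalance = r × 5.34.

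| r (assumed) | Half-width, mg/dl | Extra patients | 1-SD shift, mg/dl |
|---|---|---|---|
| 0.1 | 10.6 | 1% | 0.5 |
| 0.2 | 10.4 | 4% | 1.1 |
| 0.3 | 10.2 | 10% | 1.6 |
| 0.5 | 9.2 | 33% | 2.7 |

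These ignore the cost of estimating two slopes. With k = 2 covariates and N = 75, that cost is about k/(N − k − 3) = 2/70 = 3% of the variance. Break-even is at r² = 1 − 70/72 = 0.028, or r of about 0.17. Below that there is no net gain.

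**4. Sensitivity of sustained control.** On a linear approximation, the adjusted SE is 10.9 × √(1 − r²), and the result passes 0.05 once the difference shrinks by 21.4 − 1.96 × adjusted SE. The SD of the imbalance-driven shift is r × 10.9.

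| r (assumed) | Shrinkage needed, points | SD of shift, points | Ratio |
|---|---|---|---|
| 0.1 | 0.1 | 1.1 | 0.1 |
| 0.3 | 1.0 | 3.3 | 0.3 |
| 0.5 | 2.9 | 5.4 | 0.5 |

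An imbalance of half an SD or less would be enough. One in the other direction would strengthen the result.

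**The case against.** **Validity.** Unadjusted tests in a randomized trial are unbiased, and their intervals already allow for chance imbalance. This stands. What is lost is precision, together with the means to judge this particular allocation.

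**Size of the effect.** A reader might infer that chance imbalance in 75 patients could account for the reported differences in general. The figures do not support that. A 1-SD imbalance moves fasting glucose by 30% to 50% of the observed 5.4 mg/dl at r = 0.3 to 0.5. Matching 5.4 takes 5.4/1.60 = 3.4 SD at r = 0.3 (chance about 0.1%) or 5.4/2.67 = 2.0 SD at r = 0.5 (about 4%). The gaps in more than two hypoglycemic events (17.1 points) and in suspension of the scheme (19.7 points) are out of reach: the chance is at most 0.2% even at r = 0.7. Imbalance readily reaches only near-null differences, such as postprandial glucose (0.8 mg/dl) and any hypoglycemia (3.2 points), which are already reported as non-significant.

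**Low correlation.** Both arms titrate insulin on fasting glucose and add supplemental insulin, which may weaken the link with baseline. This stands, and is why the range starts at 0.1. For sustained control the link may be weaker still, since the listed causes of failure include early discharge, poor adherence and suspension for hypoglycemia.

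**Hypoglycemia risk factors.** It is tempting to stratify on the factors in the provision that begins "When the patient is susceptible to hypoglycemia events (localized infection". That provision is a discretionary dosing rule, not a recorded variable. Neighbouring criteria differ (localized versus soft tissue infection; filtration rate from 15 or from 16) and would have to be reconciled first. The traditional arm has only 2 patients with more than two events and 1 with suspension, so stratification offers little there.

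**Timing.** The results are printed, so no adjusted analysis can now be prespecified. This stands and shapes the remedy.

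**Conclusion.** The point holds as one about precision and transparency. The gain for fasting glucose runs from nothing useful at r = 0.1 to an interval of ±9.2 instead of ±10.7 mg/dl at r = 0.5. Even the narrower interval includes zero if the 5.4 mg/dl difference is unchanged. The conclusion most exposed is the claim of a significant difference in sustained control under intention to treat, which is borderline on its own figures and could move either way with a small imbalance. Nothing here shows that an imbalance occurred or that any reported conclusion is wrong. The size rests on the assumed r and, for sustained control, on a linear approximation. The annexes are not in this text, so a baseline table by arm may exist elsewhere.

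**What to change.** 1. Analyse fasting, postprandial and morning glucose by ANCOVA on the patient mean with arm, pre-randomization central glucose and HbA1c. State which glucose value is the covariate: eligibility refers to a fasting central value, while the baseline summary gives a random admission value.
2. Report the adjusted mean difference with its 95% CI beside the unadjusted one, and label it as added after the results were known.
3. Show baseline by arm: admission glucose, HbA1c, age, creatinine, prior treatment and service.
4. For hypoglycemia, add at most a supportive Mantel-Haenszel risk ratio stratified by one objectively recorded factor, such as age over 70.

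The cost is a paragraph of analysis text, one table and a short program. The covariates for item 1 are on the entry record sheet and those for item 3 are already summarized in pooled form, so no new data collection should be needed.
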